6.9.5 Diabetic Ketoacidosis

An assessment for DKA will be performed if a patient has any symptoms or signs that the Investigator believes may be consistent with DKA or if urine ketones are positive or blood BHB is >0.6 mmol/L. In these cases the Investigator will determine if an assessment for metabolic acidosis is appropriate and if yes, then the Possible DKA CRF will be completed.

Summary statistics by treatment group and overall for the actual values and change from Baseline in BHB based on central laboratory results will be provided by visit. Point-of-care BHB results will be listed. Similar summaries will be presented for urine ketones.

Cross-tabulation of A1C (using the following categories: $<7\%$, $\geq 7\%$ to $<8\%$, $\geq 8\%$ to $<9\%$, $\geq 9\%$ to $<10\%$, $\geq 10\%$, and overall) vs. BHB (using the following categories: 0, <0.2 , ≥ 0.2 , ≥ 0.3 , ≥ 0.5 , ≥ 0.6 , ≥ 1.0 , ≥ 2.0 , and ≥ 3.0 mmol/L) during Double-blind Treatment Period will be provided for each treatment group. In addition, cross-tabulation of A1C vs. urine ketones results will be presented.

Urine ketones cross-tabulated with BHB results will be presented for the Double-blind Treatment Period.

Total daily insulin, daily bolus insulin, and daily basal (or non-bolus) insulin, as percentage of the corresponding Baseline dose, will be cross-tabulated with BHB for the Double-blind Treatment Period. The insulin doses, in unit/kg, will also be cross-tabulated with BHB.

Incidence of BHB >0.6 mmol/L during the Double-blind Treatment Period will be analyzed by a logistic regression model adjusting for treatment, Baseline A1C, Baseline BHB, and age at T1D diagnosis (<18 years of age, ≥ 18 years of age). In addition, incidence of BHB >0.6 mmol/L during the Double-blind Treatment Period will be analyzed by a logistic regression model adjusting for treatment, Baseline A1C, change from Baseline to Week 24 in A1C, Baseline BHB, change from Baseline to Week 24 in mean daily basal (or non-bolus) insulin dose, and age at T1D diagnosis (<18 years of age, ≥ 18 years of age). Receiver operating characteristic (ROC) curves for assessing the accuracy of predictions will be presented for both logistic regression models. ROC curves will plot sensitivity vs. (1-specificity) for the prediction of BHB >0.6 mmol/L. The area under ROC curves as quantitative summary measures will be provided.

Box plots of BHB will be presented for Baseline and Week 24 visit by treatment group.

Statistical Analysis Plan

Version: Final 1.0

Lexicon Pharmaceuticals Protocol No. LX 4211.1-312-T1DM

Date of Issue: 17 MAR 2017

Covance Study ID: 000000145143

Scatter plots of A1C vs. BHB and urine ketones, and urine ketones vs. BHB will be presented for Baseline and Double-blind Treatment Period separately for each treatment group.

Scatter plots of BHB vs. total daily insulin dose, daily bolus insulin dose, and daily basal (or non-bolus) insulin dose as percentage of the corresponding Baseline dose and as units/kg will be presented for Double-blind Treatment Period by treatment group.

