^bEffective serum osmolality = $2[\text{Na}^+ \text{ (mEq/L)}] + [\text{glucose (mg/dL)}]/18]$

In the table, anion gap = $[\text{Na}^+] - [\text{Cl}^- + \text{HCO}_3^-]$ with the normal anion gap referenced as “between 7 and 9 mEq/L, and an anion gap > 10-12 mEq/L indicates the presence of increased anion gap metabolic acidosis”. However, the normal range for each of the individual measurements varies depending upon the specific methodology used. In addition, the serum potassium can be included in the anion gap measurement, resulting in a normal range that is approximately 4 mEq/L higher than the number calculated using the preceding equation. As a result, interpretation of the anion gap should be based on the laboratory reference range for the anion gap, and considering baseline values for the individual patient.

Source: Adapted from Kitabchi, 2009 [21]

The therapeutic goals in DKA management include restoration of circulatory volume and tissue perfusion, decreasing serum glucose, clearance of serum ketoacids, and correction of electrolyte abnormalities.

Instructions for the patient and site staff:

At every clinic visit blood BHB (central laboratory and point-of-care) testing will be conducted. At visits where UA is performed, the evaluation will include urine ketone determination by dipstick.

It is possible that GI or other AEs occurring with LX4211 may mask presenting symptoms of DKA (Appendix F). These symptoms include but are not limited to: inability to maintain oral intake, generalized weakness, excessive thirst, abdominal pain, nausea, vomiting, rapid weight loss, fever, frequent urination, fruity-scented breath, confusion, acute illness and/or consistently elevated blood glucose. Therefore, it is important that patients with GI complaints or intercurrent illness be instructed by the site to measure their blood or urine ketone or blood BHB levels.

(Note: In some patients alcohol may be a possible trigger for ketosis).

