The incidence rate of patients with diabetic specific laboratory results during the Double-blind Treatment Period will be presented for the following abnormality values:

- BHB >0.6, >1.0, >2.0, and >3.0 mmol/L
- Serum sodium >150 mEq/L
- Blood hematocrit >55%

Statistical Analysis Plan

Version: Final 1.0

Lexicon Pharmaceuticals Protocol No. LX 4211.1-312-T1DM

Date of Issue: 17 MAR 2017

Covance Study ID: 000000145143

- Decrease from Baseline in eGFR $\geq 25\%$

For hematology and serum chemistry, shift tables presenting movement in and out of reference range from Baseline to each scheduled post-Baseline visit will be provided for each treatment group.

Mean change from Baseline with standard error bars will be plotted by visit for select laboratory parameters for the Safety population.

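### SAP 6.9.5 models BHB only as incidence above 0.6 mmol/L and plans no between-arm estimate with a confidence interval for BHB level

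*SAP*

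**What the plan says.** **Collection.** Protocol 9.5.2: "At every clinic visit blood BHB (central laboratory and point-of-care) testing will be conducted". Protocol 5.1.4 and Appendix A place the post-Baseline visits at Weeks 4, 8, 16 and 24, and SAP Table 5.1-1 gives BHB an analysis window at each.

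**Models.** SAP 6.9.5 has two, both logistic on the same yes/no outcome.
- First: "Incidence of BHB >0.6 mmol/L during the Double-blind Treatment Period will be analyzed by a logistic regression model", with terms for treatment, Baseline A1C, Baseline BHB and age at diagnosis.
- Second: "adjusting for treatment, Baseline A1C, change from Baseline to Week 24 in A1C, Baseline BHB", plus change to Week 24 in basal (or non-bolus) insulin and age at diagnosis.

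Both come with ROC curves. SAP 7 lists the BHB logistic modelling among the changes from the protocol.

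**Descriptive output.** SAP 6.9.5 plans summaries by treatment group "for the actual values and change from Baseline in BHB based on central laboratory results will be provided by visit". It adds cross-tabulations over nine BHB categories, scatter plots, and "Box plots of BHB will be presented for Baseline and Week 24 visit by treatment group". SAP 6.9.8 adds the incidence of "BHB >0.6, >1.0, >2.0, and >3.0 mmol/L".

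**Framework.** SAP 6.8 sets out MMRM for continuous efficacy endpoints, and BHB is not one of them. The protocol synopsis (Safety Data Analysis) says that safety analysis is descriptive.

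**The concern.** The sponsor chose to go beyond description for BHB, so it is fair to ask whether the added modelling uses the data well. A yes/no at 0.6 ignores movement on either side of the cut and the number of visits at which BHB was raised. A small to moderate shift in ketone level would then rest on descriptive tables, with no adjusted estimate or interval beside them.

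Other measurements with safety meaning are treated more fully. Hypoglycemia rates get MMRM by visit (SAP 6.8.4.12), plus CMH tests at each visit and a negative binomial model (6.9.4). Serum creatinine and eGFR get MMRM (6.8.4.13). BHB, the laboratory marker used in DKA monitoring, gets one cut.

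The second logistic model does not fill the gap. Change in A1C and change in basal insulin both arise after randomisation and may lie on the path from drug to ketones. Conditioning on them removes whatever part of the effect runs through them. SAP 5.2 does not impute safety data, so a patient without Week 24 values cannot contribute to that model as specified. Only the first model's treatment term is a usable overall comparison.

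**Working it through.** **What the plan states.** It gives no BHB mean, SD, correlation, incidence or power, so there is no planned figure to reproduce. The usable inputs are 700 per arm and 20% dropout (SAP 2.3), hence 700 × 0.80 = 560 on-treatment completers per arm, and the 2-sided 0.05 level (SAP 6.1). Everything else below is assumed.

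**Assumptions for the worked case.** Log BHB is normal with correlation ρ = 0.3 between any two visits, Baseline included. The drug shifts log BHB by 0.10 in every patient, a ratio of e^0.10 ≈ 1.105. There are 560 per arm. Setting A: median 0.12 mmol/L, log SD 0.8. Setting B: median 0.20 mmol/L, log SD 0.7.

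**Step 1: any of four values >0.6.** Simulated incidences are 7.7% v 10.2% (A) and 18.7% v 23.7% (B).
- SE = √{[p₀(1−p₀) + p₁(1−p₁)]/560}
- A: SE = 0.0170, z = 0.025/0.0170 = 1.47, power = Φ(1.47 − 1.96) = 31%
- B: SE = 0.0244, z = 0.050/0.0244 = 2.05, power = Φ(2.05 − 1.96) = 54% (simulated 55%)

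**Step 2: Week 24 log BHB adjusted for Baseline.** Residual SD = σ√(1−ρ²) = σ√0.91, and SE = SD × √(2/560).
- A: SD 0.763, SE 0.0456, z 2.19, power 59%
- B: SD 0.668, SE 0.0399, z 2.51, power 71%

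**Step 3: mean of four log values adjusted for Baseline.** Residual SD = σ√[(1+3ρ)/4 − ρ²] = σ√(0.475 − 0.09) = σ√0.385.
- A: SD 0.496, SE 0.0297, z 3.37, power 92%
- B: SD 0.434, SE 0.0260, z 3.85, power 97%

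**Step 4: allow for a floor at 0.1 mmol/L.** The share of values at the floor is Φ[ln(0.1/0.12)/0.8] = 41% in A and Φ[ln(0.1/0.20)/0.7] = 16% in B. Simulation with the floor (500 replicates, Monte Carlo SE up to √(0.25/500) = 2.2 points) gave:

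| Setting | Logistic, any >0.6 | Week 24 ANCOVA | Four-visit log mean |
|---|---|---|---|
| A | 29% | 50% | 89% |
| B | 58% | 69% | 96% |

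Keeping the scale continuous at one visit gains 21 points in A and 11 in B. Averaging over visits adds a further 39 and 27. Most of the gain therefore comes from averaging.

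**Step 5: vary the assumptions.**
- 700 per arm with 20% dropout, log shift 0.10: 32-61% (any >0.6), 50-66% (Week 24), 86-98% (four-visit log mean).
- 700 per arm, ρ = 0.4, medians 0.10-0.15, log SD 0.7-0.9. A 10% rise gives 26-44% v 88-99%; 20% gives 76-94% v 100%; 30% gives 97-100% v 100%.
- Same settings, BHB multiplied by 4 in 5% of treated patients: binary 36-67%, log mean 57-78%, raw mean 84-98%. With 10% of patients affected, all three are at least 86%.

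**The case against.** The strongest reply is that a ketone effect could not disappear from the report. SAP 6.9.5 gives actual BHB and change from Baseline by arm and visit, and SAP 6.1 defines descriptive statistics to include N, mean and SD, so a crude difference and interval can be worked out from the tables. That stands. A reader might infer that the dichotomy lets a drug effect go unseen, but the documents do not support this. What is missing is a planned, adjusted estimate with its interval.

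Other points also stand:
- A reader might call 0.6 mmol/L arbitrary. Protocol 9.5.2 and Appendix F use it to define ketosis, so the logistic model answers a legitimate question: how many patients had ketosis. BHB level is a different question.
- A reader might link this to the primary endpoint. That endpoint uses positively adjudicated DKA (SAP 6.8.1), not ketosis or BHB.
- A reader might infer that early leavers are scored event-free at missed visits. SAP 6.9.5 does not define incidence, the BHB source or the handling of missed visits, and Protocol 6.3.3 allows patients who stop drug to remain in scheduled visits.
- Nothing in the documents names a 10% rise as a safety concern. A uniform ratio shift also favours the log scale; when the effect sits in a few patients, the raw mean does better.

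The rule that safety analysis is descriptive does not fully answer the point, because the SAP itself added modelling for BHB.

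**Conclusion.** The point holds in limited form. The SAP plans no between-arm estimate with a confidence interval for BHB level. The one usable modelled comparison is the incidence of BHB >0.6 mmol/L, because the second model's treatment term is conditional on post-randomisation changes.

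For a uniform rise of about 10%, power is roughly 30-60% for any value >0.6, about 50-66% for Week 24 alone and 85-98% for the visit-averaged log mean. For rises of 30% or more the choice matters little. These figures rest wholly on assumed log-normal BHB, correlation and incidence. They show the direction and rough size of the gain and do not predict this trial's result.

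This is an inexpensive improvement to an exploratory safety analysis. It does not affect the primary or secondary conclusions.

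**What to change.** In SAP 6.9.5:

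1. Keep the first >0.6 mmol/L logistic model as the answer to how many patients had ketosis. State whether incidence means any value in the period, and whether point-of-care and unscheduled values count.
2. Label the second logistic model as predictive or explanatory, and do not read its treatment term as the total drug effect.
3. Add one exploratory repeated-measures model of log central-laboratory BHB at Weeks 4, 8, 16 and 24, with treatment, time, treatment-by-time, log Baseline BHB-by-time and the three randomisation strata. Report the treatment contrast averaged over visits as a geometric mean ratio with 95% CI, with by-visit contrasts as support.
4. SAP 6.9.5 lists a BHB category of 0, which has no logarithm, and SAP 6.9.8 sets values below quantification to the limit. Prespecify a repeated proportional-odds model if many values sit at zero or the limit, with the trigger fixed before unblinding. Use non-overlapping bands built from the SAP's cut points (0, 0.2, 0.3, 0.5, 0.6, 1.0, 2.0, 3.0), and say on which side a value of exactly 0.6 falls.

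Cost: SAP wording and one more exploratory model on data already collected. The downside is that a ratio of BHB levels has little clinical meaning alone, so it must be read beside the >0.6 incidence.

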3.5 Clinical Trials of Sotagliflozin in Humans

More than 600 subjects have participated in clinical studies of sotagliflozin. No significant safety concerns have been identified in the sotagliflozin drug program, and sotagliflozin has been well-tolerated in all studies to date. Serious adverse events (SAEs) and discontinuations due to adverse events (AEs) have been infrequent and have been balanced between treatment and comparator groups. Reports of treatment-emergent adverse events (TEAEs) across all sotagliflozin studies for which data are available were generally balanced between treatment and comparator groups. Headache was reported as a possible adverse reaction that occurred in $\geq 5\%$ of subjects in sotagliflozin clinical studies, and was reported at a greater rate in sotagliflozin-treated subjects than placebo; however, most were assessed as mild to moderate, and most resolved spontaneously.

There was no common theme or imbalances in SAEs, nor were there significant imbalances between sotagliflozin and comparators in AEs. Cumulatively, during the clinical trial program 8 SAEs were reported by 6 patients (4 T2DM and 2 T1D), all of which were assessed as unrelated to study drug; those reported by 4 T2DM patients in the Phase 2 study LX4211.1-202-T2DM who received sotagliflozin included pulmonary embolism, deep vein thrombosis (DVT), bile duct stone, cholangitis and lower limb fracture, while a myocardial infarction (MI) was experienced by a patient receiving placebo. Two SAEs of diabetic ketoacidosis (DKA) were reported by 2 subjects treated with sotagliflozin in the Phase 2 T1D study LX4211.1-203-T1DM; both SAEs were assessed by the Investigator as due to failure of insulin delivery via insulin pump. In both cases, the patients had full recovery and resumed study drug within 48-72 hours of onset of DKA.

More information on the safety of sotagliflozin and on the clinical program can be found in the Investigator's Brochure.

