3.5.2 Clinical Trials in T1D

Sotagliflozin has been evaluated in a 4-week, multicenter, randomized, double-blind, placebo-controlled, proof-of-concept trial in the US (LX4211.1-203-T1DM). A total of 36 patients, 18-55 years of age, with inadequately controlled T1D with an A1C range at Baseline of 7.0-9.0% have completed the study. Prior to the double-blind portion, the trial was initiated with an open-label "pioneer" group of 3 patients, in order to determine the appropriate recommended reduction in mealtime bolus insulin.

During the double-blind expansion phase, the threshold for correction insulin to treat hyperglycemia was lowered, with patient-specific threshold and algorithm determined by the Investigators based on individual goals. The study met the primary endpoint of reduction in total daily bolus insulin, as well as exploratory endpoint of 0.55% reduction in A1C after 29 days of treatment, both of which were highly statistically and clinically significant. Two reports of DKA were reported by 2 separate patients treated with sotagliflozin. Both events were reported by the Investigators as related to pump failure and unrelated to study drug. No events of severe hypoglycemia or SAE related to hypoglycemia have been reported.

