6.2 Patient Disposition and Data Sets Analyzed

Patient disposition will be listed and summarized by treatment group and total, and will include the number and percentage of patients:

Statistical Analysis Plan

Version: Final 1.0

Lexicon Pharmaceuticals Protocol No. LX 4211.1-312-T1DM

Date of Issue: 17 MAR 2017

Covance Study ID: 000000145143

- Screened
- Did Not Enter Single-blind Placebo Run-in Phase
- Entered Single-blind Placebo Run-in Phase
- Discontinued Single-blind Placebo Run-in Phase
- Randomized
- Treated
- Completed Study
- Discontinued Study
- Included in each study population (Randomized, mITT, Safety, PP, Satiety substudy)

The number and percentage of patients who complete the study and those who discontinue early (including a breakdown of the primary reasons for discontinuation) will be presented for the patients randomized in each treatment group.

A summary of patient enrollment by center will be provided by treatment group and overall. A summary of patient counts by randomization strata (BMI, A1C, CSII) will also be provided by treatment group.

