6.9.6 Acidosis-related Adverse Events

Incidence of treatment-emergent acidosis-related AEs will be summarized to include patient counts and percentages by treatment group, and by use of CSII at Screening (Yes, No) as well, for the following: (serious and non-serious) acidosis-related AEs, serious acidosis-related AEs, non-serious acidosis-related AEs, positively adjudicated metabolic acidosis, and positively adjudicated metabolic acidosis that were also DKA.

Acidosis-related AEs are those that satisfy the trigger terms for metabolic acidosis defined in the table below. All acidosis-related AEs were adjudicated for metabolic acidosis. All cases of positively adjudicated metabolic acidosis were then adjudicated for the presence or absence of DKA.

| Trigger Terms for Metabolic Acidosis | |
|--|---|
| Trigger Terms Typically Associated With Elevated BHB | Trigger Terms That May Not Be Associated with Elevated BHB |
| Acetonaemia | Acidosis Hyperchloraemic |
| Blood Ketone Body | Metabolic Acidosis |
| Blood Ketone Body Increased | Lactic Acidosis |
| Blood Ketone Body Present | Renal Tubular Acidosis |
| Diabetic Ketoacidosis | Acidosis |
| Diabetic Ketoacidotic Hyperglycemic Coma | Uraemic Acidosis |
| Ketoacidosis | Diabetic Coma |
| Urine Ketone Body | Diabetic Hyperglycemia Coma |
| Urine Ketone Body Present | Diabetic Metabolic Decompensation |
| | Hyperglycemic Coma |
| | Hyperglycemic Seizure |
| | Hyperglycemic Unconsciousness |

The trigger terms correspond to MedDRA PTs. All trigger terms in both columns of the table will be included in the search for acidosis-related AEs, without regard to the presence or absence of an associated elevated BHB value.

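### Neither logistic model for BHB >0.6 mmol/L adjusts for CSII or BMI stratum, although both are randomisation factors and the neighbouring hypoglycemia model adjusts for them

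*SAP*

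**What the plan says.** SAP 6.9.5 plans two logistic regressions for the incidence of BHB >0.6 mmol/L during the Double-blind Treatment Period. The first "will be analyzed by a logistic regression model adjusting for treatment, Baseline A1C, Baseline BHB, and age at T1D diagnosis". The second keeps those terms and brings in two post-baseline changes; its list includes "change from Baseline to Week 24 in A1C, Baseline BHB, change from Baseline to Week 24 in mean daily basal (or non-bolus) insulin dose". Both are also to be judged as prediction models: "ROC curves will plot sensitivity vs. (1-specificity) for the prediction of BHB >0.6 mmol/L", with the area under each curve reported.

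CSII is one of three stratification factors (Protocol 6.5). SAP 6.2 names them when it plans the stratum counts: "A summary of patient counts by randomization strata (BMI, A1C, CSII) will also be provided by treatment group".

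The protocol describes two DKA cases in the Phase 2 T1D study. Section 3.5 states that "both SAEs were assessed by the Investigator as due to failure of insulin delivery via insulin pump", and section 3.5.2 that "Both events were reported by the Investigators as related to pump failure and unrelated to study drug".

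The SAP uses CSII elsewhere in safety. Acidosis-related adverse events, adjudicated metabolic acidosis and DKA are summarised by treatment group "and by use of CSII at Screening (Yes, No) as well" (SAP 6.9.6), and SAP 6.9.2 does the same for events of special interest.

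**The concern.** The SAP's other between-arm models and tests generally carry all three randomisation factors. The nearest comparator is the negative binomial GLM for hypoglycemia in SAP 6.9.4, also a supplementary safety model, which adjusts for BMI, Week -2 A1C and CSII. The two BHB models keep A1C (as Baseline A1C) and drop the other two, and the SAP gives no reason.

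CSII has some support in the documents as a candidate predictor, because both Phase 2 DKA cases were put down to the pump. SAP Section 7 lists the CSII split of events of special interest and the BHB models among the same additions to the protocol's analyses, so CSII was thought relevant to one and left out of the other.

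Two things are at stake, both modest. The ROC areas would describe prediction without a factor already recorded for every patient, and no odds ratio for pump use would be reported. The treatment odds ratio would also move slightly toward 1, because odds ratios are not collapsible over an omitted predictor.

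**Working it through.** The plan states no figure that depends on this choice, so there is none to reproduce. The check is a comparison of covariate lists, followed by an illustration on assumed inputs.

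**1. Randomisation factors in each analysis**

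| Analysis (SAP section) | BMI | A1C | CSII |
|---|---|---|---|
| CMH, binary efficacy (6.8) | yes | yes | yes |
| MMRM/ANCOVA, continuous efficacy (6.8) | yes | yes | yes |
| Satiety ANCOVA (6.8.4.15) | yes | yes | yes |
| Hypoglycemia CMH and GLM (6.9.4) | yes | yes | yes |
| BHB >0.6, model 1 (6.9.5) | no | as Baseline A1C | no |
| BHB >0.6, model 2 (6.9.5) | no | as Baseline A1C | no |

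The subgroup models (6.8.5) drop a factor only when it defines the subgroup.

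**2. Is BHB examined by CSII elsewhere?** SAP 6.9.5 cross-tabulates BHB with A1C, urine ketones and insulin dose. SAP 6.9.8 reports incidence above BHB thresholds. Neither is split by CSII. The CSII splits in 6.9.2 and 6.9.6 cover reported events. Some trigger terms in 6.9.6 concern ketone bodies, but they are adverse-event terms and not the laboratory threshold.

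**3. Size of the effect, illustration only.** The documents give neither CSII prevalence, nor the incidence of BHB >0.6, nor either odds ratio, so all four are assumptions:
- CSII prevalence q: 30, 40 or 60%
- placebo incidence r: 3, 10 or 20%
- treatment odds ratio OR_T: 2 or 4
- CSII odds ratio OR_C: 1.5, 2 or 3

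Allocation is 1:1, with CSII balanced between arms. The model has treatment t and CSII c only:

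logit p(t,c) = a + t·ln(OR_T) + c·ln(OR_C), with a set so that (1−q)·p(0,0) + q·p(0,1) = r.

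Example: q = 0.4, r = 0.10, OR_T = OR_C = 2.
- Write x = p(0,0). An odds ratio of 2 gives p(0,1) = 2x/(1+x). Solving 0.6x + 0.4·2x/(1+x) = 0.10 gives x = 0.07437.
- Then p(0,1) = p(1,0) = 0.13844. The odds of p(1,1) are 4·0.07437/0.92563 = 0.32138, so p(1,1) = 0.24322.
- Incidence on active treatment: 0.6·0.13844 + 0.4·0.24322 = 0.18035.
- Treatment odds ratio without CSII: (0.18035/0.81965)/(0.10/0.90) = 1.980. On the log scale this is 0.6833 against 0.6931, a shrinkage of 1.4%.
- AUC with treatment only: sensitivity 0.18035/0.28035 = 0.6433; false-positive rate 0.81965/1.71965 = 0.4766; AUC = 0.5 + (0.6433 − 0.4766)/2 = 0.583.
- AUC with CSII added: there are three risk levels with weights 0.30, 0.50 and 0.20 and risks 0.07437, 0.13844 and 0.24322. Events are 0.02231, 0.06922 and 0.04864; non-events are 0.27769, 0.43078 and 0.15136. Counting ties as half, AUC = (0.00310 + 0.03413 + 0.03814)/(0.14017·0.85983) = 0.625.

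Across the 3·3·2·3 = 54 combinations:
- The treatment log odds ratio shrinks by 0.1% to 6.2%. The largest shift is from 4.00 to 3.67, at q = 40%, r = 20%, OR_C = 3.
- The AUC rises by 0.019 (0.664 to 0.683) to 0.089 (0.583 to 0.672).

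The gain is over a treatment-only score. A simulation of 1400 patients (300 runs per scenario, 40% on CSII, treatment odds ratio 2.5), in which the model without CSII starts from a higher AUC, gives smaller gains: 0.678 to 0.687, 0.670 to 0.695 and 0.670 to 0.723 for CSII odds ratios of 1.5, 2 and 3. Log odds ratios without and with CSII were 0.929 and 0.934, 0.895 and 0.908, and 0.893 and 0.931. The shrinkage is therefore 0.005/0.934 = 0.5%, 0.013/0.908 = 1.4% and 0.038/0.931 = 4.1%.

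If CSII has no association with BHB >0.6, both effects are zero.

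**The case against.** The strongest case against is that this is a matter of preference in exploratory safety models.

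- The protocol points to other risks for DKA. Section 9.5.2 reports the highest occurrence in young adults (5%) and at high A1C (up to 12% at A1C ≥9%), and lists infection, intercurrent illness, stress and missed insulin as common precipitants. A1C is in both models.
- The pump evidence concerns DKA after acute pump failure. The model outcome is any BHB >0.6 mmol/L, and the covariate would be pump use at Screening. The documents do not join these.
- DKA is already split by CSII, and it enters the primary composite, whose CMH test is stratified by CSII.
- Every input to the size estimate is assumed, and the effect on the treatment odds ratio is trivial.

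Most of this stands, and it rules out stronger readings that a reader might draw. One is that pump use is the main suspected predictor of ketosis, or the only factor that the documents tie to DKA. Section 9.5.2 contradicts the second. The first would rest on two cases with no count of pump users, so no risk by pump use can be calculated. Another is that the models cannot separate drug from pump effects. Randomisation is stratified on CSII, so pump use is balanced between arms and does not confound the randomised comparison. What the models cannot do is estimate the pump association. A third is that BMI is a suspected predictor of ketosis; no section says so.

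What the objection does not remove is the inconsistency with SAP 6.9.4, the absence of any analysis of BHB by CSII, and the stated predictive use of the models. Nor is the basal-insulin term in the second model an obvious stand-in for pump problems: Protocol 3.7 reports basal insulin within 7% of baseline in both Phase 2 cases.

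**Conclusion.** The point holds as a consistency gap of low severity. Neither BHB model contains CSII or BMI stratum, no reason is given, and BHB is not examined by CSII anywhere in the SAP.

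The consequence is small. On the assumed ranges the treatment log odds ratio is attenuated by roughly 0 to 6%, which would not alter an interpretation. The clearer loss is in the ROC assessment and the unreported CSII odds ratio, and its size depends wholly on how strongly CSII is related to BHB >0.6, which the documents do not say.

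The exact calculation covers treatment and CSII only and does not reproduce either planned model. The second model also conditions on changes after randomisation, so its treatment coefficient is not a plain randomised contrast with or without CSII, and the attenuation figures should not be carried over to it.

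Both models are supplementary safety analyses added in the SAP and sit outside the testing sequence in SAP 6.8. No primary or secondary conclusion changes.

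**What to change.** In SAP 6.9.5, add CSII at Screening (Yes, No) as a covariate in both logistic models, and report its odds ratio with a 95% confidence interval beside the treatment odds ratio. Add BMI stratum (<25, ≥25 kg/m²) too, stating that this is only for consistency with the randomisation and with the hypoglycemia GLM. If either factor is to stay out, give the reason in one sentence.

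The cost is two covariates in two exploratory models. Both are already recorded for every randomised patient, so no new data are needed, and sample size and the testing hierarchy are unaffected.
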